1.4 Study Conduct

This study will be conducted in compliance with the current protocol approved by the Institutional Review Board and according to Good Clinical Practice standards. All study documents will be posted on a secure document management site. No deviation from the protocol will be knowingly implemented without the prior review and approval of the IRB except where it may be necessary to eliminate an immediate hazard to a research subject. In such case, the deviation will be reported to the IRB as soon as possible.

2 Study Objective

Our goal in this project is to demonstrate the feasibility of a novel intervention, targeted gown and glove use, to decrease SA acquisition and SA infection as a precursor for a future multisite stepped wedge cluster trial. Our targeted intervention limits both cost and stigma while blocking the transmission and acquisition of multiple organisms.

Objective 1: To implement a targeted gown and glove intervention in two community-based nursing homes.

Expected Outcome 1: A targeted gown and glove intervention can be successfully implemented across two community-based nursing homes with >80% compliance with gown and glove use for high risk care in high risk residents.

Objective 2: To evaluate the impact of a targeted gown and glove intervention on SA acquisition and SA infection rates.

Expected Outcome 2a: The intervention will decrease SA acquisition and infection rates.

Expected Outcome 2b: We will determine the effect size to guide the design (including the sample size) of a future trial.

Objective 3: To develop an implementation “toolkit” that can be easily adapted and implemented at nursing homes in a future trial.

Expected Outcome 3: Barriers to and strategies for implementation of the targeted gown and glove intervention will be identified leading to modification of the pilot intervention and development of an implementation “toolkit” for a future trial.

3 Study Design

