3.1 Primary Study Endpoints/Secondary Endpoints

Outcome 1: Compliance with each component of the intervention (identification and flagging of high risk residents, use of gowns and gloves for high risk care) based on 1) weekly point prevalence studies for high risk residents and 2) weekly observations of high risk care interactions with 5-10 residents over the 2-month intervention periods. There will also be weekly observations of high risk care interaction of 5-10 residents over the 2-month baseline period to assess the change in gown and glove use.

Outcome 2a: The primary outcome will be a change in SA acquisition rates comparing baseline and intervention periods. Residents in the nursing home will be swabbed at the start of the study period, or when they are admitted. Then they will all be re-swabbed at discharge or when the study ends. Acquisition will be defined as a positive culture for a new SA in a resident who was negative for that SA at the start of the study period or admission. Cultures will be performed in the research lab using well established methods. Specimens will be saved for future evaluation of other bacteria. The secondary outcome will be invasive SA infections and other infections within 90 days of nursing home admission in residents as detected through surveillance from health care records including but not limited to CRISP, a state-wide central repository of health care records including hospital and nursing home discharge summaries.

Outcome 2b: The observed SA acquisition rate reduction from this pilot study will be used to estimate the effect size that will inform the sample size for a larger trial.

Outcome 3: We will qualitatively examine the acceptability of, and any barriers to implementation using broad stakeholder feedback. Elements found to be infeasible or unacceptable will be modified at each stage and an implementation toolkit will be developed for the future trial.

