3.2 Study Design/Type

Study Design

We will use a quasi-experimental study of a targeted gown and glove intervention (described below) with each nursing home acting as its own control to reduce between nursing home variability.

Intervention

Our novel strategy is based on extensive prior research on the risk of *S. aureus* (SA) transmission from residents to staff gown and gloves during care interactions, the first step in transmission. Our prior work suggests a novel, evidence-based approach to preventing SA transmission and SA acquisition: targeted gown and glove use. Rather than wearing gowns and gloves for all care activities, gown and glove use could be targeted at a) specific high risk “moments” while caring for b) high risk residents. The staff interactions targeted for gown and glove use are those most likely to transmit SA to staff clothing

High risk “Moments” for Gown and Glove Use

- dressing the resident
- transferring the resident
- providing hygiene
- changing linens
- changing the resident’s brief or diaper
- device care or use
- dressing wounds

High Risk Residents

- Chronic wounds
- Invasive medical devices
- Short stay
- Totally dependent on HCW

and hands based on prior research. The targeted gown and glove use is in addition to Standard Precautions for all residents. The residents targeted are both long and short stay residents and are: 1) most likely to be colonized with SA; 2) most likely to acquire SA; 3) most likely to transmit SA to staff clothing and hands; and 4) most likely to develop a SA infection based on prior research.

Implementation Strategy

We will use a participatory approach to develop, implement, and evaluate the intervention. In other words, we will actively involve multiple stakeholders, including front-line staff and nursing home leaders in all stages of the project, including design, implementation, and evaluation.

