Serious Adverse Events that are more likely than not (probably or definitely) related to the research will be reported immediately of the site investigator becoming aware of the SAE to the local IRB according to established IRB policy. The principal investigator will evaluate the adverse event and determine whether the adverse event affects the Risk/Benefit ratio of the study and whether modification to the protocol is required.

The principal investigator will conduct a review of all serious adverse events annually. The principal investigator will evaluate the frequency and severity of the serious adverse events and determine if modifications to the protocol is required. A summary of the serious adverse events will be reported to the UMB IRB annually, when renewal is sought.

10 **Statistical Plan**

10.1 **Data Analysis, Sample Size, and Precision**

For objective 1, we will calculate point estimates and 95% confidence intervals for the rates of compliance with each component of the intervention (identification and flagging of high risk residents, use of gowns and gloves for high risk care) as well as the change in gown and glove use for high risk care during the baseline and intervention periods. We will observe 40-80 encounters per nursing home where gowns and glove should be used which will result an estimate of the rate of compliance that is accurate +/- 8-10 percentage points.

For objective 2, we will estimate and compare the rates of transmission in the baseline and intervention periods in each nursing home. To estimate the rates from binary data, we note that the risk that a person acquires the infection in the interval between swabs can be written as $1-\exp(-\lambda t)$ where “ t ” is the number of days between swabs and λ is interpretable as the daily rate of acquisition. We will estimate λ in the baseline and intervention periods using maximum likelihood estimation and compare the two rates. Likelihood methods will be used to calculate a confidence interval for the ratio of the rates. This will be done for each nursing home separately. We will test 100 residents per nursing home per period which will result in an estimate of the rate of acquisition that is accurate +/- 4-6 percentage points. These estimates will give us insight into the effect size of the intervention and the variation between nursing homes for future planning.

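### Section 10.1 specifies rate ratios per nursing home only, so the single effect size called for in Outcomes 2a and 2b has no overall estimator (minor).

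*Combined protocol and SAP*

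**What the plan says.** Section 3.1 defines Outcome 2a at study level: "The primary outcome will be a change in SA acquisition rates comparing baseline and intervention periods". Outcome 2b takes one figure forward: "The observed SA acquisition rate reduction from this pilot study will be used to estimate the effect size". Section 2 says the same under Expected Outcome 2b: "We will determine the effect size to guide the design (including the sample size) of a future trial". The study is described there "as a precursor for a future multisite stepped wedge cluster trial".

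Section 3.2 sets the design, "with each nursing home acting as its own control to reduce between nursing home variability". Section 10.1 follows that structure. It models the risk between swabs as 1 - exp(-λt), estimates λ in each period by maximum likelihood, and plans a likelihood confidence interval for the ratio of the two rates. It then says: "This will be done for each nursing home separately".

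Precision is stated for the rate: "We will test 100 residents per nursing home per period which will result in an estimate of the rate of acquisition that is accurate" to within 4 to 6 percentage points either way. The paragraph closes: "These estimates will give us insight into the effect size of the intervention and the variation between nursing homes for future planning".

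No section pools, stratifies or averages the two home-specific ratios, and none gives an expected precision for a ratio.

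**The concern.** Section 10.1 names two uses for its estimates: the effect size and the variation between homes. Separate ratios serve the second directly. For the first, the reader is left with two numbers where Outcomes 2a and 2b refer to one. The figure carried into the next trial's sample size could be either home's ratio, an average of the two, or a crude pool of all residents, and the plan does not choose among them.

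This matters because each home's ratio will be imprecise. Even if the intervention worked equally well in both homes, the two estimates could point in different directions by chance. The stated precision does not warn of this, since it concerns an acquisition risk and not the ratio.

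**Working it through.** **Inputs.** From section 10.1: 100 residents per home per period, the model risk = 1 - exp(-λt), and precision of 4 to 6 percentage points. There are two homes, so 200 residents per period when combined. The 95% level is stated in 10.1 only for objective 1 and is assumed here.

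**The plan's own figure.** No acquisition risk is given, so I solved for the risk p that matches the stated precision, using half-width = 1.96 × √(p(1-p)/100):
- p = 4.35%: 1.96 × √(0.0435 × 0.9565/100) = 4.0 points
- p = 10.5%: 1.96 × √(0.105 × 0.895/100) = 6.0 points

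The stated figure therefore fits the risk in one home in one period, if that risk is about 4.4% to 10.5%. I use 5% and 10% below, as an assumption.

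**Precision of the ratio.** With a common t, the variance of log λ is p / [(1-p) n (ln(1-p))²]. For a true ratio of 0.5, the intervention-period risk is 1 - (1-p)^0.5.
- 10% risk (5.13% in the intervention period), n = 100: variances 0.100 + 0.195 = 0.295, SE 0.543. Interval 0.5 × exp(±1.96 × 0.543) = 0.17 to 1.45.
- 5% risk (2.53%), n = 100: variances 0.200 + 0.395 = 0.595, SE 0.771. Interval 0.11 to 2.27.

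Combining two equal homes divides the SE by √2, a reduction of 1 - 1/√2 = 29%.

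| Baseline risk | SE, one home | Expected 95% CI, one home | SE, combined | Expected 95% CI, combined |
|---|---|---|---|---|
| 10% | 0.543 | 0.17-1.45 | 0.384 | 0.24-1.06 |
| 5% | 0.771 | 0.11-2.27 | 0.545 | 0.17-1.46 |

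As a check by profile likelihood, 10 versus 5 acquisitions per 100 gives 0.15-1.37 for one home. The same counts in both homes, stratified, give 0.22-1.02.

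**Chance disagreement between homes.** Give both homes the same true halving. If t is common to all residents, the direction of each estimate depends only on which period has more acquisitions, so binomial probabilities apply.
- 10% risk: P(estimate below 1) = 0.882, P(above 1) = 0.072. Opposite sides: 2 × 0.882 × 0.072 ≈ 0.13.
- 5% risk: 0.769 and 0.130. Opposite sides: 2 × 0.769 × 0.130 = 0.20.

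These percentages are approximate. The schedule in section 8.1 puts the second swab anywhere from day 1 to day 60, and the model in 10.1 uses each resident's own t, so event counts alone would not fix the direction.

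**The case against.** Estimating by home is a stated choice, tied to the own-control design and to the wish to see variation between homes. A ratio with a likelihood interval is prespecified at home level. That the study needs a single effect size is inferred from singular wording in sections 2 and 3.1. Little is foreclosed: the combined estimate only joins the two likelihoods already planned, and could be computed at analysis. Its benefit is also limited, because over the assumed risk range the combined interval for a halving still includes 1. The next trial will be a cluster trial, for which a common-effect interval may be too narrow.

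Most of this stands, and it is why the point is minor. It does not remove the gap. Outcome 2b rests on one observed reduction, 10.1 lists the effect size as an aim in its own right, and no estimator is named for it.

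A reader might infer three stronger criticisms, none of which the documents support:
- *That the per-home analysis is an error, or that the primary outcome has no planned analysis.* The analysis is specified and meets its stated purpose. Only the overall summary is missing.
- *That the precision of 4 to 6 points is wrong or misleading.* It is attached expressly to the acquisition rate, is plausible, and is not shown to be wrong. The expected precision of the ratio is simply not given.
- *That the study is too small.* Low precision is expected in a two-home feasibility study, and combining the homes does not cure it.

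**Conclusion.** The point holds as a minor gap in prespecification. Section 10.1 provides a sound estimate for each home but none for the study-level change that Outcomes 2a and 2b call for. A home-stratified ratio would cut the SE of the log ratio by 29% using data already collected, while each home remains its own control.

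The figures rest on a 5% to 10% between-swab risk inferred from the stated precision, equal t, equal baseline risk in the two homes, independent residents, and all 100 residents per home per period at risk with two swabs. Departures would mostly widen the intervals. The conclusion that no overall estimator is given rests on the text and not on these assumptions.

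**What to change.** Keep both home-specific ratios and their intervals. Then:

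1. Add to section 10.1, as the overall estimate for Outcomes 2a and 2b, one likelihood with a separate baseline rate for each home, each resident's own t, and a common intervention rate ratio, with a profile-likelihood confidence interval.
2. Beside the stated 4 to 6 percentage points, say that this applies to one home's risk in one period. Give the acquisition risk assumed and the expected interval of the combined ratio.
3. Have Outcome 2b carry forward the combined ratio with its interval together with both home-specific ratios. Note that the interval assumes independent residents and a common effect that two homes cannot verify.

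The cost is wording in section 10.1 and Outcome 2b, with no extra residents or cultures. The downsides are the uncheckable common-effect assumption and a stated precision that looks less favourable than the present one.

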12.1 Study Coordination

The University of Maryland, Baltimore will be the coordinating site for this study under the direction of the PI, [name]. It will also implement the protocol in community-based NHs in Maryland. It will coordinate study operations and be the central repository for data entry into a centralized database and perform all of the microbiology testing.

It is also responsible for training study personnel and monitoring study progress and performance. The PI and project manager will visit the NHs for a one day study start up meeting in which we review the study protocol, informed consent procedures and study procedures. In addition, the project manager will visit the NHs for study monitoring as needed during the study. We will have weekly meetings with study staff during enrollment to review performance (see below), protocol deviations and adverse events.

12.2 Performance monitoring

Study performance will be monitored via the centralized study database. The monitoring period will begin soon after enrollment begins and continue through data collection closeout. Monitoring will focus on timing, frequency and quality of study recruitment, follow-up, and data collection. Reports will be generated on a regular basis related to recruitment and data completeness. Components of the reports will include number of participants screened, number of participants enrolled, number of participants lost to follow-up, key demographics of enrolled participants, number of missing or deficient forms and summaries of data audits and edits.

12.3 Data audits

A list of completed forms for specific participants will be randomly selected from the study database on a regular basis (approximately quarterly). Hard-copies of these forms will be compared with the study database. Forms will also be inspected for proper tracking of modifications and completion of fields not captured in the study database. Discrepancies between the study forms and database and any errors found on the forms will be reported to study staff and resolution required.

APPENDIX: Study Variables**Table: Study Variables**

Ascertained				
Variables	When	How	Purpose	Format
RESIDENT CHARACTERISTICS (measured once on each subject)				
Identifying information- Name as appears in existing medical record at LTCF	Enrollment	Existing medical record at LTCF (MR)	Looking up information in MR	Nominal
Medical record number	Enrollment	MR	Looking up information in MR	Ordinal
SSN	Enrollment	MR	Looking up information in MR	Nominal
Demographics				
Level of Care	Enrollment	MR	Study variable	Nominal: Rehabilitation, Skilled Nursing, Maintenance
Short Stay	Enrollment	MR	Study variable	Yes/no
Unit in Facility	Enrollment	MR	Descriptive	Nominal: from list of units in participating LTCFs
Age	Enrollment	MR	Descriptive	Interval
Sex	Enrollment	MR	Descriptive	Nominal
Race	Enrollment	MR	Descriptive	per OMB Directive 15 definitions
Ethnicity	Enrollment	MR	Descriptive	per OMB Directive 15 definitions
Length of Stay in LTCF prior to Enrollment	Enrollment	MR	Descriptive	Interval
Charlson Co-morbidity Index	Enrollment	MR	Descriptive	Ordinal: 0-37
Dependence with ADLs	Enrollment	MR	Descriptive	Ordinal: 1 - minimal assistance, 2 - moderate assistance, 3 - requires assistance with most ADLs
Katz ADL (5)	Enrollment	MR/MDS	Descriptive	
History of colonization or infection with Multidrug Resistant Organism	Enrollment	MR	Descriptive	Yes/no
Types of Medical Devices:				
Urinary catheter	Enrollment	MR	Study variable	Yes/no
Venous catheter for parenteral medications	Enrollment	MR	Study variable	Yes/no
Gastro or jejunostomy tube for enteral nutrition	Enrollment	MR	Study variable	Yes/no
Other	Enrollment	MR	Study variable	Nominal
Type of skin breakdown:			Study variable	

Preventing the Spread of Infection in Nursing Homes

Ascertained				
Variables	When	How	Purpose	Format
Pressure ulcer	Enrollment	MR	Study variable	Yes/no
Unhealed surgical incision	Enrollment	MR	Study variable	Yes/no
Percutaneous medical device	Enrollment	MR	Study variable	Yes/no
Tracheostomy	Enrollment	MR	Study variable	Yes/no
GI Ostomy	Enrollment	MR	Study variable	Yes/no
Other	Enrollment	MR	Study variable	Nominal
HEALTHCARE SETTING FACTORS (measured once per facility)				
Facility (Study Site)	Facility Start-up		Descriptive	Nominal: from list of participating NHs
Number of Licensed beds	Facility Start-up	Administrator	Descriptive	Interval
Number of current beds	Facility Start-up	Administrator	Descriptive	Interval
Units	Facility Start-up	Administrator	Descriptive	Nominal: from list of units
Proportion of Beds- Rehab or Skilled nursing	Facility Start-up	Administrator	Descriptive	Ratio
Proportion of Beds- Short stay	Facility Start-up	Administrator	Descriptive	Ratio
Resident to staff ratio by Type of HCW and Shift	Facility Start-up	Administrator	Descriptive	Ratio
Staff Infection Control Training	Facility Start-up	Administrator	Descriptive	Yes/no; record policy
Full time employees for Infection Prevention in Facility	Facility Start-up	Administrator	Descriptive	Interval
OUTCOME VARIABLES				
SA or other Infection	Within 90 days of at admission or study period start	MR	Outcome variable	Yes/no
SA colonization of Anterior nares	At admission or study period start/discharge or study period end	Culture	Outcome variable	Yes/no
SA colonization of Inguinal skin	At admission or study period start/discharge or study period end	Culture	Outcome variable	Yes/no
STAFF/HCW OBSERVATIONS (weekly for 5-10 high risk care activities in each nursing home during both the baseline period and the intervention period)				
Gown use	Observation visits	Observation	Study variable	Yes/no
Glove use	Observation visits	Observation	Study variable	Yes/no
